Covariates: Three different adjustment sets will be used for each endpoint analysis. These include: an unadjusted model, a sex and age adjusted model, and a multivariable model with an adjustment set of: body mass index (BMI), smoking status, alcohol use, and common comorbidities: type 2 diabetes, hypertension, atrial fibrillation, angina, acute myocardial infarction, stroke, heart failure, chronic liver disease, dementia, rheumatoid arthritis, asthma, chronic obstructive pulmonary disease, chronic kidney disease, malignancy and inflammatory bowel disease.

Data sources:

The RCGP RSC is the longest running primary care network in the UK, collecting weekly data since 1964. The RCGP RSC database contains complete data on all events and clinical entities coded in UK primary care.

Study size:

The RCGP RSC cohort is drawn from a large GP practices network across England, currently covering a registered population of 2.6 million people, representing a broadly representative sample of the UK.

Data Analysis:

Cumulative lifetime incidence of AA will be estimated using cases of incident AA occurring during the observational study period (January 1, 2009 and December 31, 2018). For all analyses, the overall results including both adults (aged 18+) and children (aged 12-17) will be published, with stratification by sex, ethnicity, deprivation quintile, geographic region and urban/rural classification. The assessment of any associations with baseline characteristics and the outcomes of interest will be assessed using Cox proportional hazards models (time to event outcomes) and Poisson regression (repeated event outcomes) models. Three different adjustment sets will be used for each endpoint analysis.

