9. RESEARCH METHODS

9.1. Study design

The study will use retrospectively collected anonymised data from all eligible patients in the Oxford-Royal College of General Practitioners (RCGP) Research and Surveillance Centre (RSC) dataset at the date of data extraction. The cohort to be used for this study has already been specified for previous work as follows:

All adults and adolescents (aged 12+) registered with practices contributing data to RCGP RCS between January 1, 2009 and December 31, 2018, will be eligible for inclusion in the study. People who have opted out of record sharing will not be included (approximately 1.8% of the adult population) and have not been uploaded to the RCGP RCS database. Cumulative lifetime incidence of AA will be estimated using cases of incident AA occurring during the observational study period (January 1, 2009 and December 31, 2018). For all analyses, the overall results including both adults

(aged 18+) and children (aged 12-17) will be published, with stratification by sex, ethnicity, deprivation quintile, geographic region and urban/rural classification.

The assessment of any associations with baseline characteristics and the outcomes of interest (objectives 2-4) will be assessed using Cox proportional hazards models (time to event outcomes) and Poisson regression (repeated event outcomes) models. Three different adjustment sets will be used for each endpoint analysis. These include: an unadjusted model, a sex and age adjusted model, and a multivariable model with an adjustment set of: body mass index (BMI), smoking status, alcohol use, and common comorbidities: type 2 diabetes, hypertension, atrial fibrillation, angina, acute myocardial infarction, stroke, heart failure, chronic liver disease, dementia, rheumatoid arthritis, asthma, chronic obstructive pulmonary disease, chronic kidney disease, malignancy and inflammatory bowel disease.

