9.2. Setting

The RCGP RSC cohort is drawn from a large GP practices network across England, currently covering a registered population of 2.6 million people, representing a broadly representative sample of the UK.¹⁰

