9.2.2. Sociodemographic subgroups

Age, sex, socioeconomic status, ethnicity, major regions of England and urban/rural classification will comprise the sociodemographic factors used for stratification of the outcome measures.

Ethnicity will be grouped using the standardised definitions of major UK ethnic groups: Black, Asian, White mixed, and others.¹³

Socioeconomic status (SES) will be defined using the national deprivation measure; index of multiple deprivation (IMD) and stratified into quintiles of deprivation according to the national distribution.¹⁴ IMD is calculated at the point of data extraction, using patient postcode.

Age will be stratified into four age categories: children aged 12-17, 18-29, 30-49 and 50+ based on our previous research into incidence of AA.²

Geographical distribution will consist of two subgroups including; geographic region and urban/rural classification. Geographic region within England comprises; Greater London, South East, South West, West Midlands, North West, North East, Yorkshire and the Humber, East Midlands, and East of England.

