9.2.4. Exclusion criteria

Patients meeting any of the following criteria will not be included in the study:

1. People with the alternative non-AA diagnoses (section 9.2.1).
2. People with AA diagnosis within 6 months of registration.
3. People with less than 1 year of follow up within the dataset.
4. People over the age of 95.

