9.4. Primary Endpoints

Objective 1: An incident diagnosis of AA is the date of the first diagnosis code in the record and no alternative diagnosis that merits exclusion (any form of scarring alopecia¹², traction alopecia, congenital alopecia, androgenetic alopecia, telogen effluvium, tinea capitis, trichotillomania, or secondary syphilis of the scalp) diagnosed in the subsequent 365 days from date of AA diagnosis.

Objective 2: Mental health condition outcomes will be assessed up to two years post-AA diagnosis and will comprise new onset depressive episodes, recurrent major depression, and anxiety disorders, defined by the International Statistical Classification of Diseases and Related Health Problems 10th Revision (ICD10) classification, and identified using algorithms validated for use in UK primary care data.

Objective 3: Healthcare utilisation outcomes will comprise primary care visits, dermatology referrals, referrals for psychological therapy (including those via IAPT; Improving Access to Psychological Therapies) and psychiatric reviews in the two years post AA diagnosis.

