9.8. Data management

This study will utilise the previously extracted data from our previously published study.⁹ Individual patient data was anonymized at the point of data extraction. All data will remain in anonymized form and will be held on a secure server at the University of Oxford. The data will not be used for any purposes other than for the research which is described in the respective protocols and which has been approved by the RCGP RSC Research Committee. The sponsor, Pfizer Ltd, will not have access to the individual anonymised patient data.

All statistical analyses will be performed using R version 4.2.1.

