9.9. Data analysis

Detailed methodology for summary and statistical analyses of data collected in this study will be documented in a statistical analysis plan (SAP), which will be dated, filed and maintained by the sponsor. The SAP may modify the plans outlined in the protocol; any major modifications of primary endpoint definitions or their analyses would be reflected in a protocol amendment.

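### Poisson regression is named for repeated events with no allowance for overdispersion; with model-based standard errors, intervals for two-year primary care visits would be too narrow

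*Combined protocol and SAP*

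**What the plan says.** Section 9.1 gives the models for objectives 2 to 4 as "Cox proportional hazards models (time to event outcomes) and Poisson regression (repeated event outcomes) models". Each is to be fitted with three adjustment sets, the first of them unadjusted. The abstract repeats this: "Poisson regression (repeated event outcomes) models. Three different adjustment sets will be used for each endpoint analysis".

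Section 9.4 defines the Objective 3 endpoints: "Healthcare utilisation outcomes will comprise primary care visits, dermatology referrals, referrals for psychological therapy", together with psychiatric reviews, over the two years after diagnosis. Objective 3 is primary. Neither section 9.4 nor the variable table in section 9.3 says which outcomes are counts and which are times to a first event, although visits plainly recur within a person.

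Section 9.2.4 excludes "People with less than 1 year of follow up within the dataset". That is a minimum time in the dataset, not a minimum time after diagnosis.

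No section mentions overdispersion, a variance estimator, negative binomial regression or an offset, and the limitations in section 9.11 do not raise them. Section 9.9 leaves the detail to a separate document: "Detailed methodology for summary and statistical analyses of data collected in this study will be documented in a statistical analysis plan (SAP", which the sponsor is to hold. That SAP is not part of the supplied text.

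**The concern.** Model-based Poisson standard errors take the variance of a count to equal its mean, given the covariates. Visits by people aged 12 to 95, some healthy and some with heart failure or malignancy, are very unlikely to satisfy this. It is least likely in the unadjusted model, which leaves all variation between people in the residual.

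The study exists to describe disparities by sex, ethnicity, deprivation, region and urban/rural status. If intervals for visit rates are too narrow, chance variation between strata can be reported as a disparity. With many strata and three adjustment sets there are many opportunities for this. A separate gap is the missing statement on person-time. If follow-up after diagnosis differs between groups and no offset is used, the rate ratios themselves could be biased.

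**Working it through.** **Inputs.** From the document: Poisson regression for repeated events (section 9.1), a two-year window (section 9.4), a one-year minimum in the dataset (section 9.2.4) and 6,007 people with AA (section 9.7.1). The document gives no mean or variance for visits. Its sample-size calculation covers anxiety and depression only, so there is no plan figure to reproduce on this point. All dispersion values below are assumptions.

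**1. Closed form.** Let V be the residual variance/mean ratio. The true standard error is sqrt(V) times the model-based one. When there is no difference, a nominal 95% interval excludes 1 with probability 2 × (1 − Φ(1.96/sqrt(V))).

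| V (assumed) | sqrt(V) | 1.96/sqrt(V) | Excludes no difference |
|---|---|---|---|
| 1 | 1.00 | 1.96 | 5% |
| 2 | 1.41 | 1.39 | 17% |
| 5 | 2.24 | 0.88 | 38% |
| 10 | 3.16 | 0.62 | 54% |

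A simulation checks this: 6,007 people, one fifth against the rest, assumed mean of 8 visits, negative binomial counts with V = 3, 5 and 9. Model-based intervals covered the true value 76%, 61% and 48% of the time (closed form 74%, 62% and 49%). Sandwich intervals covered it 94% to 96% of the time.

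**2. Does adjustment remove it?** Simulation with two groups of 1,201 (6,007/5), no true difference, and a covariate score that explains part of the between-person variance in visit rate. Here k is the negative binomial shape, so that V = 1 + mean/k before adjustment. The entries show how often the model-based interval excludes no difference.

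| Setting (assumed) | 0% explained | 25% | 50% | 75% |
|---|---|---|---|---|
| mean 5, k = 4 | 20% | 16% | 12% | 8% |
| mean 10, k = 2 | 43% | 38% | 29% | 20% |
| mean 10, k = 1 | 56% | 49% | 42% | 30% |

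Adjustment reduces the problem but does not remove it in these settings. Sandwich errors gave 4.2% to 6.0% in all 24 settings run, and negative binomial regression 4.1% to 5.7% in the five checked. A single overall dispersion factor (quasi-Poisson) gave 4.6% to 10.2%, so it is less dependable.

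**3. How large are the spurious differences?** Take two groups of 1,201, mean 10, k = 2, unadjusted, so V = 1 + 10/2 = 6.
- Correct standard error of the log rate ratio: sqrt(2 × (1/10 + 1/2)/1,201) = 0.0316. The 95% limits around 1 are exp(±0.062), or 0.94 to 1.06.
- Model-based standard error: sqrt(2 × (1/10)/1,201) = 0.0129. The limits are 0.975 to 1.026.
- Closed-form false exclusion is 42%. About 5% of all estimates fall outside 0.94 to 1.06, so (42 − 5)/42, or about 88%, of the false exclusions are rate ratios within about 6% of 1.
- With k = 1 the correct limits are about 0.92 to 1.09. With k = 2 and groups a quarter of the size, the standard error doubles to 0.063 and the limits become about 0.88 to 1.13.

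**4. Other counts.** By the same formula, mean 0.3 gives 9%, 12% and 22% at k = 1, 0.5 and 0.2 (V = 1.3, 1.6 and 2.5). Mean 0.1 at k = 0.1 (V = 2) gives 17%. A low mean alone is therefore no reassurance; the unknown k decides.

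**5. Person-time.** At the same visit rate, a person observed for 1 year after diagnosis has half the expected visits of one observed for 2 years. Without an offset, a group with shorter follow-up appears to use less care.

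**The case against.** The strongest reply is that a variance estimator is ordinary SAP content. Section 9.9 defers detail to a SAP that has not been seen, and Poisson regression with robust variance is fully compatible with section 9.1. That stands: the harm is conditional on model-based errors being used. It does not remove the point, because the protocol fixes the model family and leaves open the choice on which valid intervals depend.

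It can also be said that every size is assumed, that the objectives are descriptive, and that most spurious differences in large strata would be too small to matter. All of this stands and limits the weight of the point. The direction holds whenever the variance exceeds the mean.

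Three stronger readings are tempting.
- A reader might infer that the study is committed to invalid intervals. The document does not say which standard errors will be used.
- A reader might infer that the rate ratios are biased. Overdispersion does not do that; a missing offset could.
- A reader might infer that standard errors must also be clustered by practice, here or in the Cox models. The document gives no number of practices and no within-practice correlation, and does not say that the extract holds a practice identifier. No such recommendation is made.

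**Conclusion.** The point holds as a conditional one. Poisson regression is named, no allowance for overdispersion appears in the supplied document, and model-based intervals for two-year primary care visits would be too narrow by sqrt(V). False exclusion of no difference would be about 17%, 38% and 54% at assumed V of 2, 5 and 10. The value of V in this study is unknown.

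The practical harm is overstated precision. It is modest in large strata (mostly rate ratios within about 6% of 1 in the setting shown) and larger in small ones. Other counts, including referrals, are affected to a degree that depends on their own unknown dispersion, so they cannot be assumed safe. The correction is easy and should be made before results are seen.

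**What to change.** In the SAP, and in section 9.1 if it is amended:
- Name the outcomes analysed as counts and those analysed as time to first event.
- For the counts, replace plain Poisson with Poisson regression using robust (sandwich) variance, or with negative binomial regression.
- Include the log of person-time after diagnosis as an offset, since follow-up can be shorter than the two-year window.
- Report the dispersion estimate for each count outcome, so that readers can see how much the choice mattered.

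The variance change needs no new data, since section 9.8 says "This study will utilise the previously extracted data from our previously published study" and R has standard functions for it. The cost is a few lines of text, minor programming, and wider intervals for visits and any other overdispersed count.

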9.1.1. Total disease burden; cumulative lifetime incidence

A cross-sectional design (incidence) will be used to assess the total disease burden of AA, stratified by sociodemographic groups.

9.1.2. Disparities in the impact of AA on mental health, work impact and healthcare utilisation

A matched-cohort design will be used for incidence of AA related: Mental health conditions; work impact; healthcare utilisation.

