9.3. Variables

The variables to be utilised are listed below:

Variable	Role	Operational definition
Age	Baseline characteristic, subgroup variable, and potential confounder	Age will be defined as of the index date.
Sex	Baseline characteristic, subgroup variable, and potential confounder	Identified from primary care records using clinical codes.
Socioeconomic deprivation	Baseline characteristic, subgroup variable and potential confounder	Defined using the Index of Multiple Deprivation which is divided into national quintiles.
Ethnicity	Baseline characteristic, subgroup variable, and potential confounder	Identified from primary care records using clinical codes.
UK geographic region	Baseline characteristic, subgroup variable, and potential confounder	The United Kingdom will be divided into nine regions: Greater London, South East, South West, West Midlands, North West, North East, Yorkshire and the Humber, East Midlands, and East of England. Geographic region will be captured from enrollment data.
Urban/Rural classification	Baseline characteristic, subgroup variable, and potential confounder	Defined as urban or rural area which will be captured from enrollment data.
Alopecia Areata	Case definition	Identified from primary care records using clinical codes.
Depressive episodes	Outcome	Defined by the International Statistical Classification of Diseases and Related Health Problems 10th Revision (ICD10) classification, and identified using algorithms validated or use in UK primary care data.
Recurrent major depression	Outcome	Defined by the International Statistical Classification of Diseases and Related Health Problems 10th Revision (ICD10) classification, and identified using algorithms validated or use in UK primary care data.
Anxiety disorders	Outcome	Defined by the International Statistical Classification of Diseases and Related Health Problems 10th Revision (ICD10) classification, and identified using algorithms validated or use in UK primary care data.
Dermatology referrals	Outcome	Identified from primary care records using clinical codes.
Primary care visits	Outcome	Identified from primary care records using clinical codes.
Referrals for psychological therapy	Outcome	Identified from primary care records using clinical codes.
Psychiatric reviews	Outcome	Identified from primary care records using clinical codes.

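### The multivariable adjustment set, as listed in the Abstract and section 9.1, does not name age or sex, so model 3 could be less well controlled than model 2

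*Combined protocol and SAP*

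**What the plan says.** Section 9.1 assigns Cox models to time-to-event outcomes and Poisson models to repeated events for objectives 2-4, and states: "Three different adjustment sets will be used for each endpoint analysis". The first set is empty. The other two are "a sex and age adjusted model, and a multivariable model with an adjustment set of: body mass index (BMI), smoking status, alcohol use", and the sentence then runs on through 15 named comorbidities, from type 2 diabetes to inflammatory bowel disease. The Covariates entry in the Abstract gives the same three sets in the same words.

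The variables table in section 9.3 gives age and sex each the role "Baseline characteristic, subgroup variable, and potential confounder". BMI, smoking, alcohol and each comorbidity are also labelled potential confounders there.

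Four other places bear on how age and sex are handled:

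- Section 9.1.2, on the design for objectives 2-4: "A matched-cohort design will be used for incidence of AA related" mental health, work and healthcare-use outcomes. Neither the matching variables nor the ratio is given.
- Section 9.1, on presentation of results: "with stratification by sex, ethnicity, deprivation quintile, geographic region and urban/rural classification". Age is not in this list.
- Section 9.2.2: "Age, sex, socioeconomic status, ethnicity, major regions of England and urban/rural classification will comprise the sociodemographic factors" for stratifying the outcome measures, with age in four bands of which the last is 50+.
- Section 9.9 leaves detailed statistical methods to a separate SAP, which may modify the protocol's plans. No such section is in the document, and Annex 1 lists no stand-alone documents.

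**The concern.** The three sets are called different, and the third is introduced as a set and then itemised. A programmer who follows the text would fit model 3 with BMI, smoking, alcohol and comorbidities, and without age or sex. That conflicts with the role that section 9.3 gives to both variables.

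Two things are at stake, for every endpoint of objectives 2-4 (objectives 2 and 3 are primary). First, the disparity estimates compare ethnic, deprivation, regional and urban/rural groups. If these groups differ in age or sex, and the outcome depends on age or sex, model 3 could carry a bias that model 2 removes. Second, moving from model 2 to model 3 would add one group of covariates and withdraw another. A shift in the estimate would mix the two changes and could be misread as the part explained by lifestyle and comorbidity.

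**Working it through.** The protocol gives no figure on this point, so there is none to reproduce. The check compares the texts and then illustrates the possible size with assumed inputs.

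**Step 1. Contents of the sets (Abstract and section 9.1).**

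| Model | Terms named | Age named? | Sex named? |
|---|---|---|---|
| 1 | none | no | no |
| 2 | sex, age | yes | yes |
| 3 | BMI, smoking, alcohol + 15 comorbidities = 18 terms | no | no |

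Read literally, models 2 and 3 share no term. Model 1 is nested in each, but model 2 is not nested in model 3. No wording in either place says that the third set is added to the second.

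**Step 2. Do other sections supply the missing control?**

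- *Matching (9.1.2).* The factors are not stated. If they include age and sex, matching balances people with AA against people without it. It does not balance age or sex between ethnic, deprivation or regional groups within the AA population, which is where section 8.1 places the disparity analysis.
- *Stratification (9.1 and 9.2.2).* Sex is a stratifier in both sections, age only in 9.2.2. Neither says that the ethnic, deprivation, regional or urban/rural contrasts will be cross-stratified by age.
- *SAP (9.9).* It could settle the matter, but it is not in the document.

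**Step 3. Which contrasts are exposed?** The ethnic, deprivation, regional and urban/rural contrasts: age and sex. The sex contrast: age only, because sex is then the exposure.

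**Step 4. Possible size.** Take a true ratio of 1.0 and one omitted binary covariate (for example younger age, or female sex). Let its prevalence be p1 and p0 in the two groups compared, and let g be its outcome ratio. The apparent crude ratio is

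[p1(g − 1) + 1] / [p0(g − 1) + 1].

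All inputs below are assumptions.

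| p1 vs p0 | g = 1.25 | g = 1.5 | g = 2 |
|---|---|---|---|
| 50% vs 50% | 1.00 | 1.00 | 1.00 |
| 55% vs 50% | 1.01 | 1.02 | 1.03 |
| 60% vs 50% | 1.02 | 1.04 | 1.07 |
| 60% vs 40% | 1.05 | 1.08 | 1.14 |
| 70% vs 40% | 1.07 | 1.13 | 1.21 |

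The largest entry is (0.7 × 1 + 1) / (0.4 × 1 + 1) = 1.7/1.4 = 1.21. With the groups exchanged it is 1.4/1.7 = 0.82, so the bias can go either way.

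Two intermediate cases:

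- An outcome twice as frequent at 18-29 as at older ages, with 40% against 20% of the groups in that band: (0.4 × 2 + 0.6) / (0.2 × 2 + 0.8) = 1.4/1.2 = 1.17.
- A female-to-male ratio of 1.7, with 60% against 50% women: (0.6 × 1.7 + 0.4) / (0.5 × 1.7 + 0.5) = 1.42/1.35 = 1.05.

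These are ratios for a crude comparison. Model 3 also contains covariates that may track age, so they do not estimate its residual bias.

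**The case against.** The strongest reply is that the three models form a progression, and that a reader may naturally take the third as adding its list to the second. The potential-confounder label in section 9.3 supports that intention. Section 9.9 leaves the detail to the SAP, so one cannot say that model 3 will in fact be fitted without age and sex. Model 2 is run for every endpoint, so an age- and sex-adjusted estimate will exist in any case. The protocol does not name model 3 as primary or final.

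Much of this stands. The cumulative reading is plausible, and it limits the finding to what follows if the text is taken as written. It does not remove the finding, because the text describes different sets, itemises the third and nowhere links it to the second.

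A reader might also infer that adjusting for comorbidity without age and sex undoes the balance given by matching. The documents do not support that as a general statement. The matching factors are not given, nor is it stated whether the analysis conditions on matched sets. If sets were matched on age and sex and the model were stratified by set, both would be held fixed in the comparison of AA with non-AA. That protection would not extend to comparisons between sociodemographic groups within AA.

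**Conclusion.** The finding holds as a defect in the specification: the multivariable set, as listed in both places, omits two variables that the protocol itself calls potential confounders and adjusts for in model 2. If fitted as written, model 3 could leave the disparity estimates confounded by age and sex (the sex contrast by age only), and its difference from model 2 would have no clear meaning.

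One might go further and conclude that the adjusted disparity estimates will be confounded. The documents do not support that. It would require that the literal reading is the one carried out, and that age or sex is materially unbalanced between the groups. The protocol settles neither. The range of 1.00 to about 1.2 rests entirely on assumed imbalances and outcome ratios, applies to a crude comparison and includes no bias at all. The listed covariates may absorb part of it.

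The wording should be settled before analysis, because a choice made after results are seen would be post hoc for primary objectives 2 and 3 as well as for objective 4.

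**What to change.** In the Abstract (Covariates) and in section 9.1, define the third set as: age and sex (as in the second model), plus BMI, smoking status, alcohol use and the listed comorbidities. Add that sex is omitted as a covariate where sex is the exposure. If leaving age and sex out is intended, state this and give the reason.

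In the same edit, state the matching variables in section 9.1.2, so that a reader can see which contrasts matching protects. Deprivation, ethnicity, region and urban/rural class are also labelled potential confounders in section 9.3 and appear in none of the three sets. The rewording above does not resolve that, so the plan should say which of them are adjusted for in each contrast.

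A spline for age would limit residual confounding within bands, but it is optional and not needed to correct the text.

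The cost of the main change is one phrase in two places. Age and sex are already study variables, so no new data are needed.
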